The RSV human challenge model was developed to not only aid understanding of RSV disease, but to also assess the efficacy of RSV antivirals, immunomodulators and vaccines. The RSV-A Memphis 37b challenge strain has been used for over 10 years by both hVIVO and others and has helped assess the efficacy of numerous RSV therapies and vaccines (Lambkin-Williams et al. 2018). Specifically, hVIVO have safely and successfully used the RSV challenge strain in over 1220 healthy participants (18 to 55 years of age) and have also safely completed inoculation of twenty-four participants between 60 and 75 years of age. Additionally, another strain of live RSV (Memphis 37c) has been used as an inoculation agent and was shown to be safe in over 77 healthy young adults across three studies. RSV infection was not associated with any serious adverse side effects. Healthy RSV challenge study participants have approximately 65% to 85% chance of becoming infected with RSV following the administration of the virus (DeVincenzo et al. 2010). Typical RSV illness is characterised by an abrupt onset of rhinitis, nasal stuffiness, fever, malaise, myalgia (muscle aches), and sore throat. In healthy adults, the illness usually resolves without any treatment, with relief of symptoms occurring naturally within 7 to 10 days.

Palivizumab (Synagis™), a humanised monoclonal antibody directed against RSV, has been shown to be effective in reducing hospitalisation due to RSV by approximately 50% in high-risk infants who receive monthly immunoprophylaxis. While several clinical studies with Palivizumab were performed in adults, it is not currently licensed for use in adults. A full summary of the preclinical and clinical experience with Palivizumab (Synagis™). can be found in the Summary of Product Characteristics (SmPC) and "PALIVIZUMAB Summary of relevant clinical and non-clinical data to support the use of Investigational Medicinal Product (IMP) in the clinical trial" document supplementing the SmPC.

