# 9.6.7. Efficacy Endpoint(s)

Endpoints			Planned Inferential Analysis		
Area under the viral load-time curve (VL-AUC) of RSV-A Memphis 37b as determined by qRT-PCR on nasal samples collected twice daily starting two days post-viral challenge (Day +2) up to the end of quarantine.	t-test valid	if	assumptions		
Area under the viral load-time curve (VL-AUC) of RSV-A Memphis 37b as determined by cell culture on nasal samples collected twice daily starting two days post-viral challenge (Day +2) up to the end of quarantine.					
Area under the total symptom score-time curve (TSS-AUC) collected daily in the participant symptom diary card starting one day post-viral challenge (Day +1) up to the end of quarantine.					

Endpoints	Planned Inferential Analysis
Sum Total symptom score-time curve (TSS-Sum) collected daily in the participant symptom diary card starting one day post-viral challenge (Day +1) up to the end of quarantine.	MMRM for repeated measures, if underlying assumptions valid
Total weight of nasal discharge produced starting one day post viral challenge (Day +1) up to the end of quarantine.	t-test if assumptions valid
Total number of tissues used by participants starting one day post viral challenge (Day +1) up to the end of quarantine.	
Occurrence of at least two positive "quantifiable" qRT PCR measurements in nasal samples at different timepoints reported within two or more consecutive days starting two days post viral challenge (Day +2) up to the end of quarantine.	Chi-square test
Occurrence of at least two positive "detectable" qRT PCR measurements in nasal samples at different timepoints reported within two or more consecutive days starting two days post viral challenge (Day +2) up to the end of quarantine	
Number of days with quantifiable qRT PCR measurements in nasal samples starting two days post viral challenge (Day +2) up to the end of quarantine.	t-test if assumptions valid
Peak viral load of RSV-A Memphis 37b as defined by the maximum viral load determined by quantifiable qRT PCR measurements in nasal samples starting two days post viral challenge (Day +2) up to the end of quarantine.	t-test if assumptions valid
Incidence of symptomatic RSV infection, as defined by:  o Incidence of infection, and	Chi-square test (on both the composite and each component)
o At least one grade 2 symptom from one or more respiratory categories from the participant symptom diary card.	

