### 2.3.2 Determination of sample size

#### 2.3.2.1 Part 1

Approximately 6 participants will be enrolled in Part 1 of the study for an estimated total of 6 evaluable participants. Six evaluable participants are considered sufficient to achieve the objectives of Part 1.

#### 2.3.2.2 Part 2

Approximately 50 participants will be enrolled in Part 2 of the study for an estimated total of 25 evaluable participants per intervention group.

The sample size of 50 challenged and evaluable subjects (25 Palivizumab treated subjects and 25 placebo subjects) in part 2 of the study was calculated based on the assumptions (obtained from the placebo group of prior publications of RSV challenge studies) of an infection rate of 73.7%, a mean area under the viral load-time curve (VL-AUC) of RSV-A Memphis 37b as determined by qRT-PCR on nasal samples in the placebo arm of 20.3 hours\*Log10 copies/mL with corresponding SD of 17.8 and CV of 87.9%. Based on these assumptions, and using a 0.05 two-sided type one error probability, the 50 challenged and evaluable subjects will ensure a power of 80% to the detection of a reduction of at least 70% in VL-AUC.

Using a 0.1 two-sided type one error probability, the 50 challenged subjects will ensure a power of 80% to the detection of a reduction between 60 and 65% in VL-AUC.

Reduction in VL-AUC	50%	55%	60%	65%	70%	75%	80%
N/group for 80% power, 5% two-sided	49	40	34	29	25	22	19
Power, 5% two-sided with 25 subjects	0.522	0.601	0.660	0.729	0.800	0.843	0.886
Power, 10 % two sided with 25 subjects	0.644	0.716	0.781	0.835	0.881	0.916	0.940

[figure not shown]

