### 5.1.2 Significance testing and estimation

When precised in section 5.3, between group comparisons will be performed using appropriate two-sided hypothesis tests at the 5% two-sided significance level.

For normally distributed continuous variables (either raw variable or log-transformed variables) the difference in means, the standard error and the 95% two-sided confidence interval (CI) will be presented. In case of log-transformed variables, in addition to the previous statistics on the log-transformed data, the geometric means and geometric mean ratio and its 95% two-sided CI for the original variable will be presented. The t-test, or Mixed Model for Repeated measures (MMRM) will be used, depending on the endpoint. For endpoints that are not normally distributed (such as total symptom scores), the Wilcoxon Rank-Sum test will be used.

The underlying assumptions of the MMRM presented in Section 5.4.2 will be checked by reviewing the standardized residuals ('Pearson') of the model. If necessary, splines (random coefficient linear regression spline) models will be computed and their fit compared with the fit of the linear model using AICs to address potential departure from linearity.

The underlying assumptions of the t-test will be checked by reviewing the distribution graphically and by reviewing the skewness, the kurtosis and the Shapiro-Wilks test.

For categorical variables, differences in absolute frequency and/or relative risks will be presented, with their 95% two-sided CIs will be presented. Except otherwise specified, the Chi-square test will be used to compare frequencies between groups.

P-values between 0.05 and 0.10 will be considered as indicative of a trend.

As the study is explorative by nature, there will be no attempt to adjust for the multiplicity of endpoints.

 Venn Life Sciences <small>Think Research</small>	Document Number or Project Identification: VH0001 / MB05-P-01-20
	Document Version: v3
Statistical Analysis Plan	

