**b) Objective 4:**

To estimate the margin and variance of prophylactic effect of IV treatment with Palivizumab administered 1 day prior to inoculation in the RSV human challenge model in healthy adults compared to Placebo [assessed by total symptom score (TSS)].

Sum Total symptom score-time curve (TSS-Sum) collected daily in the participant symptom diary card starting one day post-viral challenge (Day +1) up to the end of quarantine will be analysed using a MMRM if underlying assumptions valid (Statistical Table 14.2.5.5).

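### The TSS-Sum mixed model appears to use linear time (linear splines as fallback) and names no treatment contrast, so its coefficients need not measure the difference in total symptoms that Objective 4 asks for

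*SAP*

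**What the plan says.** Objective 4 is to estimate the margin and variance of the palivizumab effect on total symptom score. For TSS-Sum, SAP 5.4.2.2 b) says only that the scores from Day +1 "up to the end of quarantine will be analysed using a MMRM if underlying assumptions valid". Protocol 9.6.7 has the same content: "MMRM for repeated measures, if underlying assumptions valid". Protocol 9.6.2.2 leaves the method for each endpoint to the SAP. Neither document gives fixed effects, the form of time, a covariance structure or the contrast that measures treatment. SAP Table 14.2.5.5 is titled only as a total symptom score MMRM, for the evaluable set and the infected subgroup.

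The form of time has to be inferred from SAP 5.1.2. Model assumptions are checked on standardised residuals and, if necessary, "splines (random coefficient linear regression spline) models will be computed and their fit compared with the fit of the linear model using AICs", in order to deal with departures from linearity. TSS-Sum is the only MMRM in SAP 5.4.2, so this sentence is about that model. The same section says that differences in means with SE and 95% CI are presented for normally distributed variables, and it assigns the Wilcoxon rank-sum test to non-normal endpoints, giving total symptom scores as its example.

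**The concern.** A reference model described as linear, a spline remedy and a concern about linearity make sense only if study day enters as a continuous variable. With day as a factor there is no linearity in time to check.

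The symptom course is not linear. Protocol 2.1 describes abrupt onset, "with relief of symptoms occurring naturally within 7 to 10 days", and planned discharge is Day 12. A straight line through a rise and fall says little about its area. In a model with arm, day and arm-by-day, the interaction measures a difference in trend, and the arm coefficient measures a difference extrapolated to Day 0. Neither is the difference in total symptoms. A set of spline slopes does not give one margin with a standard error either.

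The study exists to supply margins and variances for later biosimilar evaluation (Protocol 2.2). Two analysts following this SAP could report different Objective 4 estimates. The AIC step would also let the study data decide the form in which the effect is expressed.

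**Working it through.** **The plan's own figure.** Only VL-AUC is powered: "will ensure a power of 80% to the detection of a reduction of at least 70% in VL-AUC". With mean 20.3, SD 17.8 and 5% two-sided error, the detectable difference is 0.70 × 20.3 = 14.21. Then n = 2(1.960 + 0.842)² × (17.8/14.21)² = 2 × 7.85 × 1.569 = 24.6, so 25 per group, as stated. The documents give no power, variance or curve for TSS-Sum, so what follows rests on assumed curves.

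**What a straight line extracts.** Over Days 1 to 12 the mean day is 78/12 = 6.5 and Σ(d − 6.5)² = 143. For a mean curve y(d):

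- average = Σy/12
- slope = Σ(d − 6.5)y/143
- Day-0 intercept = average − 6.5 × slope

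Take y(d) = exp(−(d − p)²/8), a bell with SD 2 days and peak on day p:

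| Peak p | Average | Slope | Day-0 intercept |
|---|---|---|---|
| 4 | 0.402 | −0.078 | 0.91 |
| 6.5 | 0.417 | 0 | 0.417 |
| 8 | 0.413 | +0.050 | 0.09 |

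A 70% reduction changes each entry by 0.7 times its value. The change in the average is nearly constant (0.28 to 0.29). The change in slope reverses sign between an early and a late peak and is zero at Day 6.5. The change in the intercept almost vanishes for a Day 8 peak.

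**Power.** Simulation with 25 per arm, Days 1 to 12, 2,500 runs per case. Assumptions: bell with SD 2 days, peak-time SD 1 day, residual SD 0.15 of mean peak height, and between-subject CV 87.9% borrowed from VL-AUC. Participant-level least-squares coefficients were compared between arms (t-test for one coefficient, Hotelling T² for joint tests); with complete balanced data this corresponds to the random-coefficient model. Entries are % power for a 70% reduction, first with normal amplitude, then with zero-inflated log-normal amplitude (73.7% infected):

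| Peak day | Average over days | Slope alone | Day-0 arm term | Joint arm + slope | Joint spline slopes, one knot |
|---|---|---|---|---|---|
| 4 | 78 / 98 | 70 / 95 | 77 / 98 | 67 / 95 | 66 / 93 |
| 5 | 79 / 98 | 56 / 81 | 74 / 97 | 69 / 94 | 67 / 93 |
| 6 | 78 / 98 | 15 / 19 | 68 / 94 | 67 / 95 | 65 / 93 |
| 6.5 | 77 / 99 | 5 / 5 | 62 / 87 | 66 / 95 | 64 / 93 |
| 7 | 77 / 99 | 15 / 18 | 51 / 77 | 66 / 95 | 64 / 92 |
| 8 | 78 / 98 | 55 / 79 | 15 / 17 | 66 / 95 | 65 / 93 |

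With no effect, every test rejects in about 4-5% of runs. A second simulation with a narrower bell (SD 1.8 days) and the effect acting on either amplitude or infection gave 82-97% for the average. Its slope term had 5-19% for a peak at Day 6 to 7 and 63-77% at Day 5 or 8.

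**Estimate.** Leaving out the interaction does not by itself repair the margin. In a further simulated check, a linear random-slope model with an arm term only returned −1.83, −0.94 and −0.75 for peaks at Day 4, 5 and 8, against true mean differences of about −1.3. The ratios are 1.83/1.3 = 1.41, 0.94/1.3 = 0.72 and 0.75/1.3 = 0.58. A covariance fitted around a misspecified line weights the days unequally.

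**The case against.** A reader might infer that the SAP tests an arm-by-time slope. It does not say so. No section specifies an interaction or makes it the test, and SAP 5.1.2 promises a difference in means with SE and CI, which points towards an average contrast. This stands: the 5-19% describes one analysis that the text permits, not the analysis that it prescribes.

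A reader might also infer that linear or spline time rules out the right contrast. It does not. With complete balanced data, the fitted arm difference at the mean day in a model with arm-by-day equals the difference in average score. The contrast only has to be named.

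Nor do splines share the large power loss: 64-67% or 92-93%, against 77-79% or 98-99% for the average. The slope term itself does well for an early peak (70% or 95% at Day 4), and the documents give no peak day.

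Finally, there are safeguards. Residual checks should expose a poor line, a Wilcoxon test is available for non-normal scores, and TSS-AUC compares total symptoms directly over the same window. TSS-Sum is secondary in an exploratory study. This limits the harm but does not supply the missing estimate. The stated remedy for a poor line is a spline, which improves fit without naming a contrast. The rank test gives no margin in score units. TSS-AUC answers Objective 3, while Objective 4 has its own table.

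**Conclusion.** The point holds in a limited form. Continuous linear time is the natural reading of SAP 5.1.2, it suits a rise-and-fall outcome poorly, and no contrast is fixed. The Objective 4 coefficient may therefore not be a difference in total symptoms. The worst case shown is a slope-only reading with a peak at Day 6 to 7: about 5-19% power for a 70% reduction, against about 77-99% for the average over days. Joint and spline tests lose roughly 5 to 15 points. These figures rest on an assumed bell-shaped curve, an assumed peak day and a CV borrowed from VL-AUC, so they show the direction and possible size, not a forecast. Type I error is not affected. The documents do not support saying that the trial would miss a symptom effect, because TSS-AUC tests total symptoms separately. The change is worth making because Objective 4 asks for a margin and the repair is cheap.

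**What to change.** In SAP 5.1.2 and 5.4.2.2 b):

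- Model the daily TSS sum with day as a categorical factor, arm and arm-by-day.
- Prespecify a parsimonious within-participant covariance, or an unstructured one with a stated fallback. Unstructured over 12 days has 12 × 13/2 = 78 parameters for 50 participants, so the fallback may well be needed.
- Name the arm difference in LS means, averaged or summed over Day +1 to planned discharge on Day 12, as the Objective 4 estimate, with SE and 95% CI.
- State how days in extended quarantine are handled, since SAP 5.2.1.2 takes discharge as actual discharge. Say also how the Day 12 sum is formed, because the diary is scheduled once that day and three times on earlier days.
- Drop the linear/spline AIC selection for this endpoint, and say when the Wilcoxon test applies to it.

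The cost is SAP wording and table programming. No data collection or sample size changes. The statistical cost is more mean and covariance parameters than a linear model, which the stated covariance rule is there to contain.

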## 5.2 Data handling conventions

### 5.2.1 Definitions

#### 5.2.1.1 Baseline

Baseline is defined as the last non-missing measurement before dosing. This will usually correspond to the measurement performed at Day-1 before first-dose, unless overruled after review of data at the DRM or otherwise stated in the appropriate endpoint section(s) below, whatever the reason for that assessment (e.g. if it is a repeat assessment, then it should be used as the baseline). However, in case of missing value at Day-1 the last available value recorded during previous visits will be used as baseline value.

If all pre-dose measurements are missing then baseline will be considered as missing, and no changes from baseline and no percentage reduction from baseline will be computed.

#### 5.2.1.2 Quarantine discharge

Unless otherwise specified, Quarantine Discharge refers to actual quarantine discharge regardless of whether discharge from quarantine occurred as scheduled on Day 12, or whether the subject entered an extended quarantine period.

### 5.2.2 Retest, Outliers

#### 5.2.2.1 Retests

The retests will be managed as follow:

- Any retest before baseline: the last available value before baseline will be used as the baseline
- Any other retest: no value will be used except if otherwise specified during the data review meeting.

#### 5.2.2.2 Outliers

All available data points will be included in analysis, unless a clear reason is available to exclude data. All outlier data will be reviewed during the data-review meeting and decisions regarding their use in the statistical analyses will be made.

### 5.2.3 Missing data and analysis rules

#### 5.2.3.1 Missing data

Missing or incomplete dates:

- For calculation / sorting / assignation based on dates (e.g., treatment emergent AEs, concomitant medications...), the following rules will apply:
- The most conservative approach will be considered (i.e., if the onset date of an AE/concomitant medication is missing / incomplete, it will be assumed to have occurred during the study treatment phase (i.e., a TEAE for AEs) except when the partial onset date or other available data indicates differently (e.g., start date day missing, but month before the month of baseline date, or stop date before baseline date).
- Medical history or disease diagnosis with missing/incomplete date will be assumed to have occurred before any study treatment except when the partial onset date or other available data indicates differently.

## Statistical Analysis Plan

- Assignations based on dates will be reviewed and confirmed or infirmed during the data review meeting
- Missing or partial start or end dates of IMP administration, if any, will be reviewed during the data review meeting.
- No other missing data will be imputed except if otherwise specified in Section 4, Section 5.3to 5.6.

### 5.2.3.2 Analysis rules

Analysis	Associated Units	Assay LLOD	Assay LLOQ	Result	Reported results	Analysis value
RSV titre (qRT-PCR)	Log10 Copies/mL	NA	2.8*	Quantifiable Titre	Value	Reported value
				DETECTED	DETECTED	LLOQ/2
				NOT DETECTED	NOT DETECTED	0
				INVALID	INVALID	Missing data point
				NOT TESTED	NOT TESTED	Missing data point
RSV titre (Plaque assay)	Log10 PFU/mL		1.7	Quantifiable Titre	Value	Reported value
				>6.04	>6.04	6.04 (ULOQ)
				DETECTED	DETECTED	LLOQ/2
				NOT DETECTED	NOT DETECTED	0
				INVALID	INVALID	Missing data point
RSV antibody titre	NAb	10	156	NDA	NDA	LLOD
				>=10 and <156	<156	LLOQ/2
				Quantifiable Titre	Value	Reported value
				≥4209	≥4209	4209 (ULOQ)
				INVALID	INVALID	Missing data point
				NOT TESTED	NOT TESTED	Missing data point

\*The LLOQ is defined as a cycle threshold (Ct) value of 33.9. This equated to 2.8 Log10 copies/mL by utilisation of a target specific copy number standard curve included in each assay run of the assay validation.

NA: Not Applicable

NDA: No Detectable Antibody

PFU: Plaque Forming Units

 Venn Life Sciences <small>Think Research</small>	Document Number or Project Identification: VH0001 / MB05-P-01-20
	Document Version: v3
Statistical Analysis Plan	

#### 5.2.4 Windows for time points

All visits will be analyzed as entered in the database except if otherwise specified during the data-review meeting.

#### 5.2.5 Unscheduled visits

Unscheduled visit measurements may be used to provide a measurement for a baseline or endpoint value if appropriate according to their definition. Other unscheduled visits data will not be analysed except if otherwise specified during data-review meeting. All data will be presented in the individual data listings and any relevant safety data will be described in the CSR.

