#### 8.7. Tympanic Temperature

The study specific normal range for tympanic temperature is detailed in Appendix 4. The severity of out of normal range values will be assigned using the DMID toxicity scale as a guide.

Temperature may be more frequently monitored in quarantine if appropriate.

Following viral challenge, pyrexia will be expected and presumed to represent virus infection consequent to viral challenge and will not be additionally captured as an AE unless it meets the definition of an AE, and is deemed to be clinically significant (in the opinion of the Investigator) to be classed as an AE.

Following viral challenge all unexpected (in the opinion of the Investigator) pyrexia will be captured as an AE, along with all other occurrences that meet the criteria for an AE.

Febrile illness (FI) is defined as any occurrence of temperature ≥ 37.9 °C

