## 9.6.9. Safety Analyse(s)

AEs will be coded using the most current version of the Medical Dictionary for Regulatory Activities (MedDRA) and summarized by system organ class, preferred term, and treatment group for the number of AEs reported and the number and percentage of patients reporting each AE.

A by-patient AE data listing including onset and resolution dates, verbatim term, preferred term, blinded treatment, severity, relationship to treatment, action taken, and outcome will be provided.

Other safety data, including laboratory evaluations (biochemistry, haematology, coagulation (if required), cardiac enzymes and urine analysis)), vital signs assessments, physical examinations, 12-lead ECG and Spirometry will be summarized by time of collection and by treatment group. In addition, change from Baseline will be summarized for vital signs and clinical laboratory results.

The frequency of patients with abnormal safety laboratory results will be tabulated by treatment.

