#### **4.2.1.5 Temperature**

Using the scheduled protocol assessments from the last assessment on Day 0 to quarantine discharge (including any extended quarantine period), this endpoint corresponds to the highest tympanic temperature.

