### 5.6.3 Laboratory safety variables

The laboratory values will be directly transferred to the data management department. The laboratory report was interpreted by the investigator. Any clinically relevant changes occurring during the trial were recorded on the AE Form of the CRF.

Laboratory evaluations will be summarized by visit and by treatment group on the SAF population (Statistical tables 14.3.4.1 to 14.3.4.12).

For each hematology, chemistry, coagulation and cardiac enzymes variables:

- Quantitative descriptive statistics will be tabulated at each time over the course of the study (e.g., at each visit) on raw values and change from baseline
- Qualitative descriptive statistics will be tabulated for each laboratory variable at each time over the course of the study by clinical significance (normal, abnormal NCS, abnormal CS) (if relevant)

All urinalysis parameters will also be analyzed as qualitative or quantitative variables per visit (Statistical table 14.3.4.13).

All laboratory results will be presented in Listings 16.2.8.

The following listings will be presented:

- Laboratory reference ranges
- Hematology
- Biochemistry
- Coagulation
- Cardiac enzymes
- Urinalysis

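### By default the SAP keeps post-baseline retests and unscheduled safety values out of its summary tables and plans no per-participant any-time count of abnormal laboratory or vital-sign values; its two temperature endpoints also use different readings.

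*SAP*

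**What the plan says.** **Retests and unscheduled values.** SAP 5.2.2.1, on retests after baseline: "Any other retest: no value will be used except if otherwise specified during the data review meeting". SAP 5.2.5 first allows some use: "Unscheduled visit measurements may be used to provide a measurement for a baseline or endpoint value if appropriate according to their definition". It then sets the default for the rest: "Other unscheduled visits data will not be analysed except if otherwise specified during data-review meeting". The same section keeps the data visible: "All data will be presented in the individual data listings and any relevant safety data will be described in the CSR". Neither section separates safety variables from efficacy variables, and neither says on what grounds the meeting would admit a value.

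**Laboratory tables.** Protocol 9.6.9 has laboratory and other safety data summarised by collection time and group. It then adds a separate sentence: "The frequency of patients with abnormal safety laboratory results will be tabulated by treatment". SAP 5.6.3 plans: "Qualitative descriptive statistics will be tabulated for each laboratory variable at each time over the course of the study by clinical significance", with the categories normal, abnormal not clinically significant (NCS) and abnormal clinically significant (CS), where relevant. The table list in SAP 11.1 contains no shift, worst-value or any-time laboratory table.

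**Vital signs and spirometry.** SAP 5.6.6 counts subjects outside limits at each time. SAP 5.6.9 gives spirometry values and changes at each time.

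**Temperature.** Protocol 8.7 foresees extra readings: "Temperature may be more frequently monitored in quarantine if appropriate". SAP 4.2.1.4 defines febrile illness as 37.9 °C or above at any time from the last Day 0 assessment to discharge. SAP 4.2.1.5 takes the highest temperature from a narrower source: "Using the scheduled protocol assessments from the last assessment on Day 0 to quarantine discharge".

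**The concern.** Off-schedule safety values are not a random sample. The protocol generates them mainly when something looks wrong:

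- Vital signs may be repeated after an unexpected out-of-range result (8.6).
- Temperature may be taken more often (8.7).
- Spirometry may be repeated for respiratory signs (8.9).
- Extra blood may be drawn to follow abnormalities (8.19), and the Part 2 schedule lets the investigator add safety assessments.

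A default that leaves these values out of the tables therefore removes readings that are more likely than average to be abnormal. By-visit counts add a second difficulty, because they cannot be summed to participants.

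Safety is a stated objective of Part 2, and Table 1 of the protocol names cardiac-enzyme and ALT/AST changes as risks of the challenge. What is at stake is a planned arm-by-arm count of participants with such abnormalities. The primary efficacy analysis is not affected.

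**Working it through.** The documents state no figure on this point, so there is none to reproduce. The check is mainly a comparison of text, plus one illustration of scale.

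**1. What the by-visit tables can tell.** Suppose a share p of an arm is abnormal at each of k scheduled draws. The share ever abnormal is then:

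- at least p (the same participants each time);
- at most k × p (different participants each time);
- 1 − (1 − p)^k if draws are independent.

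Cardiac enzymes have k = 3 scheduled post-challenge draws (Days 4, 7 and 11, Part 2 schedule). Biochemistry, which includes ALT and AST, has k = 4 (Days 4, 7, 11 and 28, leaving out the optional Day 12 draw and the Day 0 draw before challenge). The documents give no abnormality rate, so p is assumed.

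| p per draw | k = 3, range | k = 3, independent | k = 4, range | k = 4, independent |
|---|---|---|---|---|
| 2% | 2% to 6% | 5.9% | 2% to 8% | 7.8% |
| 5% | 5% to 15% | 14.3% | 5% to 20% | 18.5% |
| 10% | 10% to 30% | 27.1% | 10% to 40% | 34.4% |

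At p = 5% and k = 3, with 25 per arm, this is 25 × 0.05 = 1.25 to 25 × 0.15 = 3.75 participants (3.57 under independence). In whole participants, one abnormal result at each of three draws prints as 4% (1/25) three times, and could mean one participant (4%) or three (12%). The planned tables cannot distinguish these.

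**2. What the default rules leave out.** A participant whose only abnormal value came from an unscheduled draw or a retest appears as normal in Tables 14.3.4.3, 14.3.4.6, 14.3.4.9 and 14.3.4.12. Each such participant moves an arm's frequency by 1/25 = 4 percentage points. How many there would be cannot be derived. A related case is a cardiac-enzyme rise on Day 11, the last scheduled draw. The Day 11 value is tabulated, but a higher follow-up value would be unscheduled and is not.

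**3. Whether the AE tables close the gap.** In part. SAP 5.6.3 sends clinically relevant laboratory changes to the AE form, and protocol Appendix 3 (10.3.6.2) makes a 15% spirometry drop confirmed the same day a Grade 1 AE. The same appendix leaves challenge-associated ALT, AST, GGT and neutrophil changes to the investigator's discretion. Values judged not clinically significant do not take this route.

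**4. Which value stands after a retest.** SAP 5.2.2.1 does not say whether the first reading remains or whether both are set aside. If the first remains, a reading that the repeat showed to be a technical fault could stay in the table unless the outlier review (5.2.2.2) removes it.

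**5. Temperature.** Take a participant whose scheduled readings are all below 37.9 °C and who has one extra reading at or above it. Read literally, 4.2.1.4 makes this participant febrile in Table 14.2.10, while 4.2.1.5 gives a maximum below 37.9 °C in the highest-temperature table (5.4.2.5). SAP 5.2.5 does not resolve this, because it lets each endpoint's own definition decide and the two definitions differ.

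**The case against.** The strongest case on the other side is that this is a default set for a blinded review and nothing is lost. All data are listed, relevant safety findings must be described in the CSR, unscheduled values may serve as endpoint values, and the meeting can admit the rest before the code is broken. Summarising scheduled values and listing the others is a usual choice for a small descriptive study. By-visit layout is also the protocol's own plan, and worst-value counts depend on how often people are retested. Most of this stands, and it rules out several stronger readings that a reader might infer:

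- *That the SAP discards the data.* It does not, for the reasons above.
- *That all safety is tabulated only by visit.* AE tables cover the whole study, QTc category counts are not stated to be by visit, and febrile illness and highest temperature cover the whole quarantine period after challenge.
- *That the promised abnormality frequency is not produced.* It is planned for each visit, and protocol 9.6.9 does not say at any time.
- *That troponin peaks between Days 4, 7 and 11 are lost through the SAP.* A peak on a day without a draw is not measured, and no table can recover it. Only values from actual extra draws are at issue.

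The objection does not supply preset criteria for the meeting or a planned arm-level count for abnormal values outside the AE tables. Nor does it reconcile the two temperature definitions. Because 9.6.9 gives the patient frequency in its own sentence, after the by-time summaries, a count of patients is the more natural reading, and SAP section 8 records no departure from it.

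**Conclusion.** The point holds in a limited form. By default, post-baseline retests and unscheduled safety values stay out of the summary tables, and admission is left to a meeting without preset criteria. No planned table gives the number of participants per arm ever abnormal on laboratory tests or vital signs. The likely undercount is confined to abnormal values that are not clinically significant, and to challenge-associated changes such as ALT/AST that the investigator does not record as AEs. Its size is unknown. The 5% to 15% range for three draws rests on an assumed 5% rate and shows only that by-visit counts do not determine the any-time count. Spirometry is the weakest example, since confirmed drops reach the AE tables. The temperature mismatch is real but narrow. It requires an off-schedule reading of 37.9 °C or above with every scheduled reading lower. The changes should be made, but the efficacy conclusions do not depend on them.

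**What to change.** 1. In SAP 5.2.2.1 and 5.2.5, exempt safety variables from the exclusions, and state which value represents a visit when a retest exists.
2. In SAP 5.6.3 and 5.6.6, add a table on the safety analysis set, by arm, of participants with any abnormal post-dose value (and, for laboratory tests, any CS value), counting scheduled, unscheduled and confirmed repeat values. Keep the by-visit tables.
3. Use the same set of readings for highest tympanic temperature and febrile illness, and say so in 4.2.1.4 and 4.2.1.5.

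The cost is SAP wording and a few tables from data already collected. There is a small downside. Any-time counts depend on how often participants are retested, and they may look slightly less favourable. Since retesting is done blind to treatment, this should not in itself favour either arm.
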